**Overall Objective:**

The purpose of this prospective randomized clinical trial is to compare two currently accepted standard-of-care treatment strategies: medical thoracoscopy as compared to instillation of intrapleural tissue plasminogen activator (TPA) and human recombinant deoxyribonuclease (DNase) for the management of complicated pleural infections in adults as defined as complicated parapneumonic effusions or pleural empyema.

**Introductory Statement and Background:**

Pleural infection (empyema or complex parapneumonic effusion [CPPE]) represents one of the common clinical diagnoses encountered in clinical practice in the United States (US) and worldwide. The incidence of pleural infection continues to rise with an annual incidence of approximately 65,000 in the US and United Kingdom (UK). It is associated with substantial morbidity and mortality as well as increased hospital costs despite advances in medical diagnostic and therapeutic strategies. The overall mortality of pleural infection approaches 20% and it is above 30% in elderly patients over 65 years and immunocompromised patients.

Treatment of CPPE or empyema requires antibiotics and drainage of the pleural cavity. However, in about 30% of cases, it is difficult to remove the fluid due to loculations, septations and increased viscosity of the pleural fluid, and around 20% will need surgical intervention to adequately treat the pleural infection.

**Rationale:**

The intrapleural therapy of combined tissue plasminogen activator (tPA) and human recombinant deoxyribonuclease (DNase) in the management of pleural infection has been shown to improve the chest radiographic appearance at day 7 in the Multi-center Intra-pleural Sepsis Trial (MIST2). However, this approach is expensive, with a substantial hospital stay (around 12 days), and had a no significant decrease in the rate of surgery referral as compared to placebo.

Although two randomized studies have shown that around 80% of patients with pleural infection can be successfully managed medically, early surgical intervention is still considered a first-line treatment for pleural infection in some regions around the world. This approach has been justified on the basis of improved clinical outcome and shorter hospital stays for patients managed in this way.

Video-assisted thoracoscopic surgery (VATS) has been suggested as a surgical invasive approach to clear potentially infected material from the pleural space. In one small randomized and another non-randomized prospective trial comparing VATS with intercostal drainage plus intrapleural streptokinase, VATS was associated with decreased hospital stays and overall costs. However, there are several limitations that need to be mentioned. First, these two trials were under-powered studies without appropriate sample size calculation. Second, VATS was compared to intrapleural streptokinase. The intrapleural activity of endogenous plasminogen activator inhibitor (PAI-1) in the pathogenesis of pleural infection is important since this mediator not only directly inhibits streptokinase but has also been shown to contribute to the severity of loculation and poor outcomes with intrapleural fibrinolytic therapy. Third, large case series have shown that VATS is usually performed on a younger and less comorbid population (i.e. highly selected patients), compared to the unselected population of patients (which are usually sicker, elderly and have multiple comorbidities) with pleural infection seen in the fibrinolytic studies. Moreover, failure to respond to medical fibrinolytic therapy might

necessitate invasive surgical intervention, such as VATS, or even open thoracotomy, at a later stage of the pleural infection where adequate clearance of the dense septations and thickening within and around the pleural cavity is needed to reverse lung restriction and improve compliance. However, clinical outcomes are unpredictable, with some patients having no long-term sequelae but others showing permanent impairment of lung function.

Medical thoracoscopy (MT) is a minimally invasive procedure that can be used to treat pleural infection through improving clearance by mechanical adhesiolysis and targeted drain placement. MT can also be used in patients who are not fit for general anesthesia by using local anesthesia and sedation. MT has shown to be safe and effective in the treatment of pleural infection in observational studies. However, to date, there are no randomized controlled trials addressing the potential role of early MT versus fibrinolytic therapy in empyema and complicated pleural infection.

**Proposal:**

**Specific Aim 1:**

To compare the efficacy of early medical thoracoscopy versus fibrinolytic therapy (tPA/DNase) in patients with complicated parapneumonic effusions or pleural empyema.

**Methods and Procedures:**

**Study Design**

This prospective randomized trial will be conducted at UF Health Shands Hospital in accordance with Good Clinical Practice Standards and under IRB supervision. A large number of patients with pleural infection are treated at our institution, with a multidisciplinary team comprised of experienced interventional pulmonologists, chest radiologists and thoracic surgeons. We plan to enroll a total of 60 patients with pleural infection that will be randomized utilizing a computerized system to either medical thoracoscopy (thoracoscopy group) or fibrinolytic therapy (fibrinolytic group).

**Patient Population**

Subjects (> 18 years of age) with either CPPE or empyema will be screened for inclusion.

Screening logs recording reasons for non-trial entry will be kept.

CPPE is defined as non-purulent effusion in a patient with clinical evidence of infection such as fever and/or elevated blood leukocyte count and/or elevated CRP, with pleural fluid pH  $\leq$  7.2 (measured by blood-gas analyzer), or pleural fluid glucose < 60 mg/dl or pleural fluid LDH >1000 IU/L. Empyema is defined as pus within the pleural space and/or presence of bacteria on pleural fluid Gram stain or culture.

For patients to be considered for the trial they need to fulfill one of the following criteria: 1) CPPE along with evidence of septated pleural effusion on pleural ultrasonography and/or chest CT scan (Figure 1) or 2) empyema.

[figure not shown]

Figure 1. Thoracic ultrasound showing complex pleural effusion along with septation (arrowhead)

Prescreening / Study exclusion criteria are as follows:

- 1) age <18 years;
- 2) pregnancy
- 3) inability to give informed written consent;
- 4) previous thoracic surgery or thrombolytic therapy for pleural infection;
- 5) medical thoracoscopy cannot be performed within 48 hours;

- 6) inability to tolerate procedure due to hemodynamic instability or severe hypoxemia;
- 7) inability to correct coagulopathy;
- 8) presence of a homogeneously echogenic effusion on pleural US (Figure 2).

[figure not shown]

Figure 2. Thoracic ultrasound showing homogeneously echogenic loculated effusion

Patients who agree to participate in the trial will sign an informed consent. Next, all patients will undergo diagnostic thoracentesis as per standard of care. In addition to standard of care testing on pleural fluid, an additional 10 mLs of fluid will be collected to check for markers like interleukin-8 and vascular endothelial growth factor. All patients will receive intravenous antibiotics according to local hospital guidelines and local microbiology results. Intravenous antibiotics will be changed to oral consolidation therapy by the managing consultant in light of the clinical response. Antibiotic therapy will be continued for between 2 and 6 weeks, as required per standard of care.

Following diagnostic thoracentesis and confirmation of pleural infection, participants will be randomly assigned to either receive thoracoscopy (treatment arm) or fibrinolytic therapy (control arm). (Figure 3)

Pleural effusion will be defined as loculated if it (1) has a lobulated shape with a convex border or (2) it is compartmentalized or accumulated in a fissure or a non-dependent portion of the pleura. On chest ultrasound the pleural effusion will be defined as loculated if it has fibrin

strands or septa floating inside the anechoic/hypoechoic pleural effusion(s) along with the presence of defined multiple pockets in the pleural cavity.

Pain scores and general physical status will be assessed using a participant-completed 100-mm visual analog scale (VAS) upon randomization, at 6 weeks (via phone call) and 12 weeks follow up.

### **Study Protocol I- Thoracoscopy (Treatment Arm)**

Patients will undergo medical thoracoscopy (rigid or semi-rigid) within 48 hours of randomization. A single port (with a maximum of 2 ports) will be placed and thoracoscopy will be performed under monitoring as per standard protocols, with the patient in a lateral decubitus position. The pleura will be carefully inspected through the thoracoscope under direct visualization. Adhesiolysis will be attempted and pleural irrigation will be done. At the end of the procedure, a drain will be inserted and connected to an underwater seal with a negative pressure suction. As per standard of care, a chest CT without contrast will be performed when chest tube drainage is < 75 mLs and if there was no evidence of significant pleural effusion (<200 ml), the catheter will be removed. The fluid volume will be calculated by measuring the maximum perpendicular distance between the surface and the chest wall right above the diaphragm with at maximum inspiration in the most dependent position. Any need for additional drainage or administration of fibrinolytic or surgery will be considered treatment failure.

### **II-Fibrinolytic Therapy (Control Arm)**

A chest tube (14-French or less) will be inserted under ultrasonography into the most dependent area of the pleural effusion or into the largest loculation in patients with multi-loculated effusions. The dose of DNase (Pulmozyme, Genentech, USA) will be 5 mg and the dose of tPA (Actilyse, Genentech, USA) will be 10 mg, each in 50 ml of 0.9% NaCl. The tPA and DNase will not be mixed together in one syringe. Concurrent tPA and DNase will be administered intrapleurally through the chest tube followed by saline flush. The tube will then be clamped for 120 minutes and after which it will be connected back to wall suction. The intrapleural therapy will be given twice daily for a maximum of 6 doses. As per standard of care, a chest CT without contrast will be performed when chest tube drainage is < 75 mLs and if there was no evidence of significant

pleural effusion (<200 ml), the catheter will be removed . Any need for additional drainage or more doses of fibrinolytic from the existing drainage over and above the 6 doses mentioned or surgery will be considered treatment failure.

## **Study Outcome**

### **Primary outcome measure:**

- Duration of hospital stay after intervention, as defined as thoracoscopy in the treatment arm and first dose of fibrinolytic in the control arm

### **Secondary outcome measures:**

- Number of days with chest tube drainage
- Total length of hospital stay
- Failure rate of assigned treatment necessitating intervention defined as any of the following:
  - 1-Surgical intervention (VATS, open thoracotomy) in either arm
  - 2-Need of additional chest tube and/or fibrinolytic therapy in the medical thoracoscopy arm due to clinical non-responsiveness
  - 3-Need of additional chest tube in the fibrinolytic therapy arm due to clinical non-responsiveness
- Adverse events
  - Pleural bleeding defined as drop in serum hematocrit requiring blood transfusion or causing hemodynamic instability
  - Significant pain requiring escalation of analgesia
- In-hospital and 30-day mortality
- Change in pleural fluid volume on chest CT scan from randomization (day 0) to prior to chest tube removal measured by radiologist ([name]) blinded to treatment allocation using image J software. Volume of pleural effusion will be obtained by examination of radiographic images obtained during the standard-of-care CT examination.
- Infectious biomarker (CRP) from randomization (day 0), at removal of chest tube and 12 weeks as per standard of care
- Total costs of each treatment modality in each treatment site

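### Treatment failure is defined in two conflicting ways: the arm descriptions count events whatever the reason, while the secondary outcome counts fewer events and filters most of them by an undefined reason

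*Combined protocol and SAP*

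**What the plan says.** Three places in the combined protocol and SAP say what counts as treatment failure.

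- **Study Protocol I, Thoracoscopy (Treatment Arm):** "Any need for additional drainage or administration of fibrinolytic or surgery will be considered treatment failure". No reason is required.
- **II, Fibrinolytic Therapy (Control Arm):** the events counted as failure are "Any need for additional drainage or more doses of fibrinolytic from the existing drainage over and above the 6 doses mentioned or surgery". Again no reason is required.
- **Secondary outcome measures:** the reported outcome is "Failure rate of assigned treatment necessitating intervention defined as any of the following", followed by three items. Item 1 is "Surgical intervention (VATS, open thoracotomy) in either arm". Item 2 is "Need of additional chest tube and/or fibrinolytic therapy in the medical thoracoscopy arm due to clinical non-responsiveness". Item 3 is "Need of additional chest tube in the fibrinolytic therapy arm due to clinical non-responsiveness".

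The only blinding described is for the radiologist who measures fluid volume on CT, "blinded to treatment allocation using image J software". The section on sample size and statistical analysis does not say which definition of failure will be analysed.

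**The concern.** The outcome list looks like a restatement of the two arm rules, but it is narrower. It makes an extra tube in either arm, and fibrinolytic in the thoracoscopy arm, count only when attributed to clinical non-responsiveness. That term has no criteria, no named judge and no adjudication. An observable event thus becomes one that counts only with an assigned reason. The two treatments are plainly distinguishable at the bedside, so the person assigning the reason very probably knows the arm.

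The list also drops a criterion that the control arm section states outright, namely doses beyond 6. At stake is the comparison of how often each strategy needed something further. The Risks and Benefits section names reduced need for later treatment among the outcomes that the study should clarify. If the definition is settled only once data are in hand, the failure rate can depend on which section the analyst follows.

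**Working it through.** The documents give no expected rate, effect size, power or sample size for the failure outcome, so there is no planned figure to reproduce. The check is a comparison of the three texts, followed by the arithmetic of one reclassified patient.

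**Comparison by event**

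| Event | Arm description | Secondary outcome list |
|---|---|---|
| VATS or open thoracotomy, either arm | Failure | Failure (item 1, no filter) |
| Second chest tube for residual fluid on CT in a stable patient, either arm | Failure | Failure only if attributed to non-responsiveness |
| Fibrinolytic in the thoracoscopy arm | Failure | Failure only if attributed to non-responsiveness |
| Control patient given more than 6 doses through the existing drain, nothing else | Failure | Not listed |
| Further drainage by a route other than a chest tube | Failure | Not listed |
| Rescue thoracoscopy (control arm) or repeat thoracoscopy (treatment arm) | Not named; could fall under drainage or surgery | Not named; could enter through its drain if attributed to non-responsiveness |

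Three things follow.

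1. Every event named in the outcome list is also a failure under the arm descriptions, but not the reverse. In each arm, the rate under the outcome list can only equal or fall below the rate under the arm description.
2. The mismatch on doses beyond 6 needs no reading of non-responsiveness at all, and it affects the control arm only. Item 2 can count fibrinolytic against the thoracoscopy arm, whereas item 3 never counts extra fibrinolytic against the control arm.
3. The second-tube case is realistic, because both arms use CT and a 200 ml threshold to decide on drain removal.

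**Size of one reclassification**

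- Input: total enrolment, from Study Design: "We plan to enroll a total of 60 patients with pleural infection". The sample size section gives 30 per group; 60 / 2 = 30.
- Change in an arm's failure rate for k patients classified differently: k / 30.
- k = 1: 1/30 = 3.3 percentage points. k = 2: 2/30 = 6.7 points. k = 3: 3/30 = 10.0 points.

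The documents do not say how large k would be. That requires the rate of failures that do not end in surgery, which is not given.

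**The case against.** **The outcome list may be meant as the operative definition.** On this reading the arm descriptions are looser narrative, and the qualifier is a sensible way to leave out tubes replaced for mechanical reasons. Such a filter is legitimate if it is defined. But it is not defined, no section is given precedence, and the arm descriptions state in plain terms what will be considered failure. The reading also leaves the omission of doses beyond 6 unexplained.

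**Rescue thoracoscopy.** A reader might infer that a control patient rescued by medical thoracoscopy would go uncounted. The documents do not show this. The thoracoscopy section says that a drain is left at the end of the procedure, so item 3 may well capture the patient, and the bracketed surgical procedures in item 1 can be read as examples. What stands is that the procedure is unnamed everywhere and its handling is uncertain.

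**Who judges.** No section says that unblinded treating staff assign the reason. It is an inference, though a reasonable one, given that blinding is described only for the CT reader.

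**Magnitude.** It is tempting to take the roughly 20% surgery figure from the background section, treat it as 6/30, and say that recoding two patients gives 4/30 = 13.3% or 8/30 = 26.7%. This does not follow. Surgery is item 1 and carries no filter, so those six patients cannot be recoded out, and nothing in the documents supports adding two others. Likewise, Fisher's exact test gives p = 0.25 for 2/30 against 6/30 and p = 0.042 for 2/30 against 9/30, so three reclassified patients could in principle carry a comparison across 0.05. All those counts are assumed, and they are not evidence of what would happen here.

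**Residual judgement.** Removing the reason filter does not remove all unblinded judgement, since clinicians still decide whether to place a tube. That is correct: the change removes one layer of judgement, not all of them.

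**Conclusion.** The point holds as an inconsistency in the definition of a reported secondary outcome. The arm descriptions and the outcome list classify some patients differently: those with a further tube or, in the thoracoscopy arm, fibrinolytic not attributed to non-responsiveness; control patients given more than 6 doses; and patients drained other than by chest tube. Rescue and repeat thoracoscopy are unresolved in all three places.

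The supported size is 3.3 percentage points in an arm's failure rate per patient classified differently, assuming the planned 30 per arm. The number of such patients, and the net effect on the difference between arms, cannot be derived. A reader might infer a bias toward one treatment. The documents do not establish one: the omission of doses beyond 6 can only lower the control rate relative to that arm's own rule, but the reason filter operates in both arms. The primary outcome, hospital stay after intervention, does not depend on this definition. The change should be made, but it does not threaten the main analysis.

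**What to change.** Reconcile the two arm descriptions and the secondary outcome list into one definition, and state that it is the one analysed. The simplest version carries the event-based rule of the arm descriptions into the outcome list. A patient is then a failure on any of:

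- any additional drainage, in either arm;
- any fibrinolytic in the thoracoscopy arm;
- fibrinolytic beyond the 6 protocol doses in the control arm;
- surgery, in either arm.

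Drop the reason filter. State explicitly how rescue thoracoscopy in the control arm and repeat thoracoscopy in the treatment arm are counted. Record the reason for each event as a descriptive field, and add a sensitivity analysis that excludes purely mechanical tube replacements. If the sponsor prefers to keep a reason filter, it needs written objective criteria and adjudication blinded to allocation.

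The cost is a wording change and one data field. The downside is that some mechanical replacements count as failures in the main analysis; the sensitivity analysis shows how much that matters. The change concerns classification of the outcome only and alters no treatment.

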#### **Risks associated with thoracoscopy:**

- a.** Chest pain (5%). The nerves between the ribs are bruised after the procedure, which can cause some persistent pain.
- b.** Air leak from lung (1-5%). A small hole develops in the lung. This means the chest tube has to stay in longer.
- c.** Bleeding (< 1%). Usually it is minor and settles quickly. Bleeding is more common if you have been taking blood thinning drugs.
- d.** Heart problems (< 1%). A brief minor strain may be put on the heart. This can cause abnormal beating of the heart, fluid to accumulate in the lungs, a heart attack, or the heart may stop beating.
- e.** Low oxygen levels (< 1%). Participants will be administered oxygen if needed.
- f.** Death(< 1%) as a result of this procedure is uncommon.

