#### **Risks associated with fibrinolytic therapy:**

- a. Pain (15%)-While the medications are in the pleural space, participants may feel some discomfort. Usually such pain can be relieved by analgesics.
- b. Bleeding (5%)-While medications are in the pleural space, participants may experience bleeding inside the pleural space. Usually, it resolves with stopping medications. Rarely, blood transfusion might be need or require surgery.

**Privacy risks:** As with any study, there is a risk that personal health information, collected during the course of research, may be disclosed. The research team will do everything within their power to mitigate and minimize this risk. The data collected both written and electronic will be held securely in a locked cabinet and secure server behind the UF Health firewall respectively. Only the study individual will be contacted and the questionnaires' administered in the privacy of a secluded clinic room. The data collected will be restricted to only the minimum amount necessary to accomplish the aim of the study.

[figure not shown]
**Risks associated with psychological stress:** Participants may feel embarrassed or uncomfortable responded to questions. Participants will be informed that they may refuse to answer any of the questions and may take a break at any time during the study. Participants are also free to withdraw from the study at any time.

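### The adverse-event outcome covers both harms listed for fibrinolytic therapy but omits air leak, cardiac, low-oxygen and sedation harms listed for thoracoscopy

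*Combined protocol and SAP*

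**What the plan says.** The protocol's Secondary outcome measures place two sub-items under adverse events: "Pleural bleeding defined as drop in serum hematocrit requiring blood transfusion or causing hemodynamic instability" and "Significant pain requiring escalation of analgesia". No time window is given for them. Death is a separate secondary outcome, "In-hospital and 30-day mortality".

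The risk sections list more:

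- **Fibrinolytic therapy** has two clinical risks: "Pain (15%)-While the medications are in the pleural space, participants may feel some discomfort" and "Bleeding (5%)-While medications are in the pleural space, participants may experience bleeding inside the pleural space".
- **Thoracoscopy** has six: chest pain (5%), air leak (1-5%), bleeding (<1%), heart problems (<1%), low oxygen levels (<1%) and death (<1%). Of chest pain the protocol says: "The nerves between the ribs are bruised after the procedure, which can cause some persistent pain".
- **Sedation** risks include respiratory depression and low blood pressure, with no rates. The Rationale describes sedation in connection with medical thoracoscopy. The chest-tube risk section mentions only local numbing.
- **Chest tubes and thoracentesis** have their own lists, including tube infection (<5%) and collapsed lung. Both procedures apply to both arms.

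No other section sets up wider adverse-event collection. Study Design refers to Good Clinical Practice and IRB supervision. The visual analog scale under Patient Population covers pain and general status at randomization, 6 weeks and 12 weeks.

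**The concern.** A safety comparison is fair when the harms expected from each strategy have the same chance of being recorded. Here the outcome covers everything the protocol expects from fibrinolytics and only part of what it expects from thoracoscopy. Supervision by an IRB does not supply the rest, because events reported that way do not become a pre-specified comparison between arms.

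The Significance section says the results could change practice, so readers will want to weigh any shorter stay against procedural harm. Air leak is the clearest gap. The protocol itself says it prolongs chest-tube time, so it would lengthen an efficacy outcome without being recorded as a complication. A reader could not then tell a procedural injury from slow drainage.

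**Working it through.** The plan states no figure to reproduce here. The check matches each listed risk to the outcomes, then applies the protocol's rates to 30 patients per arm (Sample Size and Statistical Analysis).

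**1. Coverage**

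| Listed risk | Listed for | Rate | Captured? |
|---|---|---|---|
| Pain | Fibrinolytic | 15% | Yes, if analgesia is escalated |
| Bleeding | Fibrinolytic | 5% | Yes, if the definition is met |
| Chest pain | Thoracoscopy | 5% | Yes, if analgesia is escalated |
| Bleeding | Thoracoscopy | <1% | Yes, if the definition is met |
| Death | Thoracoscopy | <1% | Yes, under mortality |
| Air leak | Thoracoscopy | 1-5% | No |
| Heart problems | Thoracoscopy | <1% | No |
| Low oxygen | Thoracoscopy | <1% | No |
| Respiratory depression, low blood pressure | Sedation | none given | No |

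Coverage by the adverse-event outcome is 2 of 2 for fibrinolytics and 2 of 6 for thoracoscopy (3 of 6 with mortality).

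**2. Size of the uncounted thoracoscopy harms** (taking <1% as 0 to 1%)

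- Low end: 1% + 0 + 0 = 1%; 30 × 0.01 = 0.3 patients.
- High end, summed: 5% + 1% + 1% = 7%; 30 × 0.07 = 2.1 patients.
- High end, assuming independence: 1 − 0.95 × 0.99 × 0.99 = 6.9%; 30 × 0.069 = 2.1 patients.
- Chance of at least one air leak among 30 patients: 1 − 0.99^30 = 26% at a 1% rate, and 1 − 0.95^30 = 79% at a 5% rate.

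Sedation harms would add to these figures but cannot be quantified from the protocol.

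**3. Does counting them change the direction?** (patients with any listed harm, independence assumed)

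- Fibrinolytic: 1 − 0.85 × 0.95 = 19.25%.
- Thoracoscopy, counted harms only: 5% with bleeding near 0, and 1 − 0.95 × 0.99 = 5.95% with bleeding at 1%.
- Thoracoscopy with the uncounted harms, low end: 1 − 0.95 × 0.99 = 5.95%. The gap moves from 19.25 − 5 = 14.25 to 19.25 − 5.95 = 13.3 points, a change of about one point.
- Thoracoscopy with the uncounted harms, high end: 1 − 0.95 × 0.99 × 0.95 × 0.99 × 0.99 = 12.4%. The gap moves from 13.3 to 19.25 − 12.4, or about 6.8 points.

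The listed risks stay higher for fibrinolytics throughout.

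**The case against.** The strongest reply is that bleeding and pain are the harms common to every procedure in the trial. The protocol lists both for thoracoscopy, chest tubes and thoracentesis as well as for fibrinolytics, so they are a natural basis for comparison. This stands. A reader might infer that the outcome was built from fibrinolytic harms alone, and the documents do not support that.

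A reader might also infer that the outcome could by itself make thoracoscopy look safer, or that full counting would halve the gap between arms. Neither is established. Near-halving needs air leak at 5% and the <1% risks at a full 1%; at the low end the change is about one point. The plan defines no composite of any adverse event, so that gap is not a quantity the trial would report as written. The listed rates also include milder events than the outcome definitions: discomfort during instillation is not the same as pain that needs more analgesia.

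Tube infection is uncounted too, but both arms receive a drain, so its omission is not part of the asymmetry. Death is already captured. A prolonged air leak would show indirectly in tube days and length of stay, though not as a complication.

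Finally, the adverse-event item does not say its list is closed, whereas the treatment-failure item does. The two sub-items could be read as merely those needing a definition. Even so, the plan would not say which other events are collected, how, or over what period.

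**Conclusion.** The point holds in a limited form. As written, the adverse-event outcome uses two shared harms and leaves out air leak, cardiac events, low oxygen and sedation harms. Among the strategy-specific risks the protocol lists, every omission falls on the thoracoscopy side, so the incompleteness runs in that arm's favour.

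The uncounted harms with stated rates affect about 1% to 7% of thoracoscopy patients, or 0.3 to 2 per 30. This assumes that the listed rates apply to this trial, that sedation is mainly a feature of the thoracoscopy arm, and that fibrinolytic patients do not have the same events at a similar rate. The protocol lists no such risk for fibrinolytic therapy, but only collection in both arms would show it. The figures are indicative and do not support a claim that the safety conclusion would reverse.

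**What to change.** In Secondary outcome measures, add these adverse-event components:

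- air leak or pneumothorax
- cardiac events
- hypoxaemia or respiratory depression
- sedation-related hypotension

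Give each a definition and a collection window, identical in both arms. Report every item by arm, together with the number of patients with at least one event. Tube or pleural infection can be added for completeness, since it applies to both arms. Death stays under the existing mortality outcome.

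This is a cheap improvement: a few case-report-form fields and one more table row per harm, with no extra patients. The drawback is sparse data. Cardiac and low-oxygen events, for example, are each expected in at most 30 × 0.01 = 0.3 thoracoscopy patients. The added rows will support description and not formal testing, and the plan should say so.
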